### Latent TB

Latent tuberculosis	Mycobacterium tuberculosis complex	Tuberculin test false negative
Mycobacterium test positive		Tuberculin test positive

Herpes zoster infection		
Colitis herpes	Herpes zoster	Herpes zoster meningoencephalitis
Gastritis herpes	Herpes zoster cutaneous disseminated	Herpes zoster meningomyelitis
Genital herpes zoster	Herpes zoster disseminated	Herpes zoster necrotising retinopathy
Herpes oesophagitis	Herpes zoster infection neurological	Herpes zoster oticus
Herpes ophthalmic		
Herpes pharyngitis	Herpes zoster meningitis	Herpes zoster pharyngitis
Herpes sepsis		
Herpes virus infection		

Meningitis herpes  
Meningomyelitis herpes  
Ophthalmic herpes  
zoster  
Pneumonia herpes viral  
Proctitis herpes  
Varicella zoster gastritis  
Varicella zoster  
oesophagitis  
Varicella zoster  
pneumonia  
Varicella zoster virus  
infection

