 - Clinical laboratory assessments will include blood chemistry, hematology, urinalysis, coagulation and the acute phase proteins (CRP, ESR, and fibrinogen) as well as change from baseline in these laboratory parameters.
 - Adverse events (including serious adverse events, infections, injection site and hypersensitivity reactions).

Immunogenicity:

- Determination of anti-ALX-0061 antibodies (ADA) and potentially further characterization by modified ADA (mADA) assay and neutralizing antibody (nAb) assay.

Statistical Methods:

This is an OLE study and is not set by statistical power. Subjects with active RA who have completed the 24-week (study ALX0061-C201) or 12-week (study ALX0061-C202) treatment and assessment period of one of the preceding phase IIb studies with ALX-0061, who were randomized to the placebo or ALX-0061 arms in the preceding studies, and who achieved at least 20% improvement in SJC and/or TJC (66/68 counts) at the final visit of the preceding study, will be invited to participate in the extension study. Up to a maximum of approximately 501 subjects will participate in this OLE study. Subjects who enrolled in this OLE study will be included in the safety and efficacy analyses.

Statistical analyses are considered descriptive.

SCHEDULE OF ASSESSMENTS ^A

Study Period	Screening/Baseline, Treatment and Assessment period (Weeks)												Early Termination ^c (Weeks)	Follow-up (Weeks)
	Screening/ Baseline ^B 0	4	8	12	24	36	48	60	72	84	96	104		
Study Visit ^D	1	2	3	4	5	6	7	8	9	10	11	12	2 (after last study drug administration)	12 (after last study drug dosing)
Visit Number														13
Ambulatory visit	X	X	X	X	X	X	X	X	X	X	X	X		X
Written informed consent	X													
Review of entry criteria	X													
Smoking history	X													
Study drug injection card dispensation	X													
Study drug administration (via interactive web response system [IWRS]) ^E	X	← Injections to continue every 2 weeks up to and including Week 102 →												
Physical examination	X ^B			X	X	X	X	X	X	X	X	X		X
Vital signs ^F	X ^B	X	X	X	X	X	X	X	X	X	X	X		X
Tuberculosis (TB) evaluation (questioning) ^G	X ^B			X	X	X	X	X	X	X	X	X		X
Routine clinical laboratory analyses ^H	X ^B	X	X	X		X		X		X	X			X
Extended clinical laboratory analyses (including fasting serum lipids) ^I	X ^B				X		X		X			X		
Pregnancy test (urine) for females of childbearing potential only.	X ^B			X	X	X	X	X	X	X	X	X		
Morning stiffness duration	X ^B												X	X

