A similar summary table will be produced for all TEAEs including those of the parent trials (C201 and C202). Any event happening either on parent trial or on the current trial will be considered for deriving the number and percentage of subjects with at least one event, and the number of events. The incidence per 100 patient years will be calculated as:  $100 \times (\text{Number of subjects with AE}) / (\text{Total number of years observed starting from the first dose in parent trial, summed for all subjects})$ .

Another summary table will be presented selecting adverse events of special interest. Search criteria for these adverse events can be found in section 16.5.

The following categories will be included in the summary table:

- infection
- serious infection (requiring hospitalization or i.v. antimicrobial treatment)
- opportunistic infection, excluding TB
- active TB infection
- latent TB infection
- Herpes zoster infection
- malignancy
- hypersensitivity reaction (including anaphylaxis and angioedema)
- hypersensitivity reaction (including anaphylaxis and angioedema) leading to withdrawal
- GI perforation
- demyelinating disorder
- MACE

This table will represent events which occurs only after the first dose of study drug in C203 study.

One more summary table for AEs of special interest will be produced including events from the parent trials as well. Any event happening either on parent trial or on the current trial will be considered for deriving the number and percentage of subjects with at least one event, and the number of events. The incidence per 100 patient years will be calculated as:  $100 \times (\text{Number of AEs}) / (\text{Total number of years observed starting from the first dose in parent trial, summed for all subjects})$ .

Tables by SOC and PT will report the number and percentage of subjects with at least one event, occurring only after the first dose of study drug on C203 study. Percentages will be calculated out of the number of subjects in the relevant treatment group.

These tables will be prepared for the following selections of AEs:

- TEAEs
- TEAEs by severity (Mild, Moderate, Severe)
- TEAEs with an incidence of at least 3%
- serious TEAEs
- non-serious TEAEs
- study drug-related TEAEs
- study procedure-related TEAEs
- TEAE for which the study or the study drug were discontinued

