## 16.5 Appendix 5: Search criteria for adverse events of special interest

Search criteria for AESIs are either MedDRA PT clusters or SMQs. The SMQs and the individual PTs for the PT clusters are provided below. The MedDRA version used for the data coding is v21.0.

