Oesophageal candidiasis	Proctitis herpes	Varicella zoster gastritis
Ophthalmic herpes zoster	Progressive multifocal leukoencephalopathy	Varicella zoster oesophagitis
Opportunistic infection	Progressive vaccinia	Varicella zoster pneumonia

Adrenal gland tuberculosis	Male genital tract tuberculosis	Tuberculosis liver
Bone tuberculosis	Meningitis tuberculous	Tuberculosis of central nervous system
Choroid tubercles	Oesophageal tuberculosis	Tuberculosis of eye
Congenital tuberculosis	Pericarditis tuberculous	Tuberculosis of genitourinary system
Conjunctivitis tuberculous	Peritoneal tuberculosis	Tuberculosis of intrathoracic lymph nodes
Cutaneous tuberculosis	Prostatitis tuberculous	Tuberculosis of peripheral lymph nodes
Disseminated tuberculosis	Pulmonary tuberculoma	Tuberculosis ureter
Ear tuberculosis	Pulmonary tuberculosis	Tuberculous abscess
Epididymitis tuberculous	Renal tuberculosis	central nervous system
Erythema induratum	Salpingitis tuberculous	Tuberculous endometritis
Exposure to communicable disease	Silicotuberculosis	Tuberculous laryngitis
Extrapulmonary tuberculosis	Spleen tuberculosis	Tuberculous pleurisy
Female genital tract tuberculosis	Thyroid tuberculosis	Tuberculous tenosynovitis
Joint tuberculosis	Tuberculosis of central nervous system	
Lymph node tuberculosis	Tuberculosis	
	Tuberculosis bladder	
	Tuberculosis gastrointestinal	

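### The PT list that defines active TB in SAP Appendix 5 includes an exposure term that is not TB, and the herpes zoster row mixes in unspecified herpes terms without saying so

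*SAP*

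**What the plan says.** SAP 7.1 plans a summary table of AESIs. Its categories include "active TB infection", latent TB infection and "Herpes zoster infection", each as its own row. On how events are assigned to rows it says: "Search criteria for these adverse events can be found in section 16.5". Appendix 5 (SAP 16.5) opens with: "Search criteria for AESIs are either MedDRA PT clusters or SMQs". The TB and zoster rows are of the first kind, explicit lists of PTs. Neither section describes a medical review, adjudication or confirmation step.

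The TB list that stands between the opportunistic infections list (which excludes TB) and the latent TB list includes "Exposure to communicable disease". The list headed herpes zoster infection includes "Herpes virus infection" and "Herpes pharyngitis" alongside terms that name zoster.

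These lists feed Table 14.3.1.3 (events after the first C203 dose) and Table 14.3.1.4 (parent-trial events added). Both show subjects, events and incidence per 100 patient-years.

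**The concern.** A PT list used without case review is the case definition: an event coded to a listed term is a case. If the active TB list holds a term that does not describe tuberculosis, the SAP's rule counts a non-case as active TB. This row may have few events or none, and it will be read closely for a drug acting on the IL-6 pathway. The protocol itself treats TB as important: it is an exclusion criterion (3.2.2) and a reason to stop study drug (3.2.3.2).

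The zoster row raises a weaker form of the same question. A reader who sees a row labelled herpes zoster will take every event in it to be zoster, but part of the list only says herpes.

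**Working it through.** The plan gives no figure to reproduce here. The check is a reading of the two lists, a count, and one calculation for scale.

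**Which list is active TB.** The text as read shows no heading above the TB list; it was probably lost in conversion and is not held against the plan. Three things identify the list:
- Its content is tuberculosis at various sites.
- It stands after opportunistic infections excluding TB and before latent TB.
- SAP 7.1 gives its rows in the same order: opportunistic excluding TB, active TB, latent TB, herpes zoster.

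**TB list.** There are 43 distinct PTs. Two contain no tuberculosis word: the exposure term and erythema induratum. Erythema induratum is not counted against the plan: judging it needs outside knowledge, and it does appear in the SAP's general Infections cluster. The exposure term describes contact rather than illness and is not specific to TB. In the alphabetical Infections cluster it would fall between exanthema subitum and Exserohilum infection, and it is not there. A subject whose only relevant event had this PT would therefore count as active TB but not as having an infection. Deleting it leaves 43 − 1 = 42 PTs.

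**Zoster list.** There are 27 PTs. Those that do not name zoster are: colitis herpes, gastritis herpes, herpes oesophagitis, herpes ophthalmic, herpes pharyngitis, herpes sepsis, herpes virus infection, meningitis herpes, meningomyelitis herpes, pneumonia herpes viral and proctitis herpes. That is 11 of 27, or 41%. The other 27 − 11 = 16 name zoster.

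**Scale of one misclassified event.** The inputs are the maximum enrolment of about 501 (SAP 3.2; Protocol 3.6.8) and the maximum duration of 114 weeks per subject (Protocol 3.1.1).
- Patient-years = N × 114 / 52.18. For N = 501: 501 × 114 / 52.18 ≈ 1,095.
- Added rate = 100 / patient-years = 100 / 1,095 ≈ 0.09 per 100 patient-years.
- If only 200 to 400 subjects were followed for the full period (an assumption), patient-years would be about 437 to 874 and the addition about 0.23 to 0.11.

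Early discontinuation shortens follow-up and raises the figure. Table 14.3.1.4 counts time from the first parent-trial dose, so its denominator is larger and the addition smaller.

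**The case against.** **The zoster list may be deliberately broad.** This has force. The opportunistic infections cluster holds many PTs that name herpes simplex, and none is in the zoster list. So the list drops what is known to be simplex and keeps what could be zoster, which is a defensible sensitive search in a descriptive, single-regimen study. A reader might infer that the 11 terms are wrong diagnoses. The documents do not support that: the terms are unspecified, and an imprecisely reported zoster case could be coded to one of them. What remains is that the SAP does not state this intention and the row label carries no caveat. Nor is the breadth consistent, since genital, oral and nasal herpes and herpes dermatitis are in the Infections cluster but not in the zoster list.

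**An exposure may never reach the adverse event data.** The Schedule of Assessments provides for TB evaluation by questioning, from which a reader might infer that exposures will be actively elicited and recorded as events. The documents do not show this. They do not give the questions, and neither the adverse event definition (Protocol 3.5.1) nor the reporting criteria (3.4.4.1) mention exposure. Those criteria are not exhaustive and leave room for investigator judgement, so such a record is possible, but its likelihood is unknown.

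**A false count could be traced.** This also stands. Table 14.3.1.5 shows every event by system organ class and PT, and Listing 16.2.7.1 gives verbatim term and PT. Because TB requires permanent stopping of study drug, a true case should also appear in Table 14.3.1.12. A false active TB count could thus be explained, but the summary row and its rate would still be wrong as printed.

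**Conclusion.** The TB point holds. Under the rule as written, an event coded to the exposure term counts as active TB, and nothing in the SAP would remove it. This rests on identifying the unheaded list as the active TB list, for which the evidence is strong, and on the absence of any stated case review.

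The zoster point holds only as a labelling matter: 11 of 27 PTs are unspecified, and the row does not say so.

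The importance is minor. No event counts are given, so neither a percentage inflation of zoster nor a false TB signal can be claimed. The only supportable size is about 0.09 per 100 patient-years per misclassified event at maximum enrolment and follow-up. That is small in absolute terms, though it would be the entire active TB rate if there were no true case. The analyses are descriptive, and no test or decision rule is tied to these rows.

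**What to change.** 1. Delete the exposure PT from the active TB list in SAP 16.5. No information is lost, since an event so coded still appears in the system organ class and PT table and in the adverse event listing.
2. For herpes zoster, either relabel or footnote the row in Tables 14.3.1.3 and 14.3.1.4 as including unspecified herpes terms, or keep the list and show how many of its events come from the 16 PTs that name zoster. Either choice keeps the sensitivity of the present search.

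The cost is one deleted term and one footnote or extra row. No data collection changes.

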**Malignancies**

Malignancies standardized MedDRA query (SMQ) (Narrow)

**Hypersensitivity reactions (including anaphylaxis and angioedema)**

Anaphylactic reaction SMQ (Narrow)

Angioedema SMQ (Narrow)

Hypersensitivity SMQ (Narrow)

**Gastrointestinal (GI) perforation**

Gastrointestinal perforation SMQ (Narrow)

**Demyelinating disorders**

Demyelination SMQ (Narrow)

**Major adverse cardiac events (MACE)**

Cardiac failure SMQ (Narrow)

Cerebrovascular disorders SMQ (Narrow)

Ischemic heart disease SMQ (Narrow)

# Your Health and Well-Being

---

This survey asks for your views about your health. This information will help keep track of how you feel and how well you are able to do your usual activities. *Thank you for completing this survey!*

For each of the following questions, please mark an  in the one box that best describes your answer.

**1. In general, would you say your health is:**

Excellent	Very good	Good	Fair	Poor
 1	 2	 3	 4	 5

**2. Compared to one week ago, how would you rate your health in general now?**

Much better now than one week ago	Somewhat better now than one week ago	About the same as one week ago	Somewhat worse now than one week ago	Much worse now than one week ago
 1	 2	 3	 4	 5

3. The following questions are about activities you might do during a typical day. Does your health now limit you in these activities? If so, how much?

Yes, limited a lot	Yes, limited a little	No, not limited at all
▼	▼	▼

- a Vigorous activities, such as running, lifting heavy objects, participating in strenuous sports.....  1.....  2.....  3
- b Moderate activities, such as moving a table, pushing a vacuum cleaner, bowling, or playing golf.....  1.....  2.....  3
- c Lifting or carrying groceries .....  1.....  2.....  3
- d Climbing several flights of stairs .....  1.....  2.....  3
- e Climbing one flight of stairs .....  1.....  2.....  3
- f Bending, kneeling, or stooping .....  1.....  2.....  3
- g Walking more than a mile .....  1.....  2.....  3
- h Walking several hundred yards.....  1.....  2.....  3
- i Walking one hundred yards .....  1.....  2.....  3
- j Bathing or dressing yourself .....  1.....  2.....  3

**4. During the past week, how much of the time have you had any of the following problems with your work or other regular daily activities as a result of your physical health?**

	All of the time	Most of the time	Some of the time	A little of the time	None of the time
	▼	▼	▼	▼	▼

- a Cut down on the amount of time you spent on work or other activities .....  1 .....  2 .....  3 .....  4 .....  5
- b Accomplished less than you would like .....  1 .....  2 .....  3 .....  4 .....  5
- c Were limited in the kind of work or other activities .....  1 .....  2 .....  3 .....  4 .....  5
- d Had difficulty performing the work or other activities (for example, it took extra effort) .....  1 .....  2 .....  3 .....  4 .....  5

**5. During the past week, how much of the time have you had any of the following problems with your work or other regular daily activities as a result of any emotional problems (such as feeling depressed or anxious)?**

	All of the time	Most of the time	Some of the time	A little of the time	None of the time
	▼	▼	▼	▼	▼

- a Cut down on the amount of time you spent on work or other activities .....  1 .....  2 .....  3 .....  4 .....  5
- b Accomplished less than you would like .....  1 .....  2 .....  3 .....  4 .....  5
- c Did work or other activities less carefully than usual .....  1 .....  2 .....  3 .....  4 .....  5

6. During the past week, to what extent has your physical health or emotional problems interfered with your normal social activities with family, friends, neighbors, or groups?

Not at all	Slightly	Moderately	Quite a bit	Extremely
				
 1	 2	 3	 4	 5

7. How much bodily pain have you had during the past week?

None	Very mild	Mild	Moderate	Severe	Very severe
					
 1	 2	 3	 4	 5	 6

8. During the past week, how much did pain interfere with your normal work (including both work outside the home and housework)?

Not at all	A little bit	Moderately	Quite a bit	Extremely
				
 1	 2	 3	 4	 5

- 9. These questions are about how you feel and how things have been with you during the past week. For each question, please give the one answer that comes closest to the way you have been feeling. How much of the time during the past week...**

	All of the time	Most of the time	Some of the time	A little of the time	None of the time
	▼	▼	▼	▼	▼

- a Did you feel full of life? .....  1 .....  2 .....  3 .....  4 .....  5
- b Have you been very nervous? .....  1 .....  2 .....  3 .....  4 .....  5
- c Have you felt so down in the dumps that nothing could cheer you up? .....  1 .....  2 .....  3 .....  4 .....  5
- d Have you felt calm and peaceful? .....  1 .....  2 .....  3 .....  4 .....  5
- e Did you have a lot of energy? .....  1 .....  2 .....  3 .....  4 .....  5
- f Have you felt downhearted and depressed? .....  1 .....  2 .....  3 .....  4 .....  5
- g Did you feel worn out? .....  1 .....  2 .....  3 .....  4 .....  5
- h Have you been happy? .....  1 .....  2 .....  3 .....  4 .....  5
- i Did you feel tired? .....  1 .....  2 .....  3 .....  4 .....  5

- 10. During the past week, how much of the time has your physical health or emotional problems interfered with your social activities (like visiting with friends, relatives, etc.)?**

	All of the time	Most of the time	Some of the time	A little of the time	None of the time
	▼	▼	▼	▼	▼
	 1	 2	 3	 4	 5

**11. How TRUE or FALSE is each of the following statements for you?**

Definitely true	Mostly true	Don't know	Mostly false	Definitely false
▼	▼	▼	▼	▼

- a I seem to get sick a little easier than other people.....  1 .....  2 .....  3 .....  4 .....  5
- b I am as healthy as anybody I know.....  1 .....  2 .....  3 .....  4 .....  5
- c I expect my health to get worse .....  1 .....  2 .....  3 .....  4 .....  5
- d My health is excellent .....  1 .....  2 .....  3 .....  4 .....  5

***Thank you for completing these questions!***

SF-36v2® Health Survey © 1992, 1996, 2000 Medical Outcomes Trust and QualityMetric Incorporated. All rights reserved.

SF-36® is a registered trademark of Medical Outcomes Trust.

(SF-36v2® Health Survey Acute, United States (English))
